Participants will be recruited at the time of their routine +BHN study visit, at which comprehensive information about their current health status, function, quality of life, cognitive concerns, and cognitive performance is already being gathered. Following informed consent, all participants will complete a short set of neuropsychological tests and questionnaires that have been shown to be sensitive to the effects of GMT [Sustained Attention to Response Task-SART (18),Tower of London (19), and Dysexecutive Questionnaire-DEX (20)] immediately, or at a visit arranged for this purpose, separate from the +BHN main study. Participants will then begin GMT, as described below. Within 4 weeks of completing the GMT program, they will be asked to repeat the neuropsychological testing and complete additional tests which form part of the standard +BHN visit at a second study visit, coincident with the +BHN study visit if timing permits.

Intervention

The standard GMT program lasts 9 weeks and involves 9 weekly 2-hour small group sessions led by a trained therapist. It follows a manualized program that teaches participants a series of techniques to build attention and executive function, and shows them how to implement these techniques in their everyday life. The small group sessions allow individualization of the training to show how it can be applied to

meet the particular challenges reported by participants, and explicitly encourage participants to share their challenges and successes with others in the group to promote learning and engagement with the program. The sessions are reinforced with homework, in which participants practice what they have learned. Sessions will be audiotaped for later review by the trainer and/or study investigators to ensure adherence to the intervention manual. The material, including homework, is provided in a workbook that participants use throughout the training, and keep for later reference.

TREATMENTS

There are no pharmacological treatments involved in the current study.

STUDY EVALUATIONS/PROCEDURES

Informed Consent

The subject will be asked to read and sign the approved informed consent form prior to any assessments being performed. Sufficient opportunity will be given to discuss the study and consider the information in the consent process prior to agreeing to participate. The original signed informed consent form will be retained in the subject's study files and a copy will be provided to the subject.

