Subject Identification Number Assignment

Subject Identification (ID) numbers assigned for the core platform will be used for this sub-study.

DETAILS OF STATISTICAL ANALYSIS

Analysis and Sample Size

The feasibility and acceptability of the GMT will be evaluated in the whole group (N=30) based on the proportion of GMT sessions attended, the proportion of the homework completed, and the overall level of satisfaction with the program, as determined by an anonymous questionnaire filled out by the participants at the end of the intervention.

The potential impact on cognition of GMT will be evaluated in two ways: (i) a within-person analysis of change in cognitive outcomes after all persons have completed the GMT program; and, for exploratory purposes, (ii) a between group comparison contrasting change in cognitive outcomes between the GMT group and the concurrent control group assessed in the main study.

For all analyses, the B-CAM (performance measure) will be the primary cognitive outcome and a global outcome response will be based on changes in the B-CAM and on four secondary cognitive outcome measures: SART, Tower of London, Dysexecutive Questionnaire-DEX and PDQ.

For the within-person analysis, change from pre-to post will be calculated for each person and a 95% confidence interval (CI) around the mean change will be calculated. A 95% CI that excludes 0 indicates statistically significant change. A sample size of 30 will provide 80% power to detect an average standardized response mean (effect size for change) of 0.38, within the reported range for GMT in other conditions. However, average change is not very interpretable as this average change can occur in many ways including no change for a lot of people and large change for a few, or even deterioration for some. To provide a more interpretable estimate of treatment impact, an overall effect will also be reported, based

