on the proportion of individuals who improved at least 0.5 SD on one of the cognitive outcome measures. A change of 0.5 SD is considered clinically relevant (21). For this analysis, generalized estimating equations (GEE) will be utilized to adjust for a possible correlation between the different measures. The outcome will be the binary response for each of the five cognitive outcomes, and the analysis yields an estimated charge proportion adjusted for non-independence. Having five outcome measures increases the number of observations available for analysis by a factor of 1.8, termed the design effect. The design effect (22) is a function of the number of measures (here m-1) and the correlation between measures (estimated at 0.2). Hence the number of observations effectively available for analysis is 30 x 1.8 or 54. With this sample size, the 95% CI will exclude a low responder proportion (20%) as long as the responder proportion is greater than 28% (www.vassarstats.net).

For the between-group analysis, 30 people in the intervention group and a concurrent control group of 100 (with five outcome measures, the effective sample size is inflated by the design effect of 1.8). Thus, using all measures, the sample would provide 80% power to detect an effect size of 0.4 (0.4 of a SD). For this analysis, generalized estimating equations (GEE) for a continuous outcome will be utilized to adjust for a possible correlation between the different measures. Each measure will be transformed onto a 0 to 100 scale for permit a global intervention effect to be estimated.

REFERENCES

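### The only post-test is timed from completing GMT, so people who stop early have no planned assessment and the within-person estimate becomes completers-only by default

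*Combined protocol and SAP*

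**What the plan says.** Under STUDY DESIGN, Procedure, participants take SART, Tower of London and DEX at baseline, then start GMT. The follow-up rule is "Within 4 weeks of completing the GMT program, they will be asked to repeat the neuropsychological testing". The same visit adds tests from the standard +BHN battery, and it coincides with the cohort visit if timing allows. No other post-test is scheduled, and no rule covers a person who stops attending.

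Under Analysis and Sample Size, effect is assessed first by "a within-person analysis of change in cognitive outcomes after all persons have completed the GMT program". The between-group comparison is labelled exploratory. The first of these is computed as follows: "change from pre-to post will be calculated for each person and a 95% confidence interval (CI) around the mean change will be calculated". On outcomes, "the B-CAM (performance measure) will be the primary cognitive outcome", with SART, Tower of London, DEX and PDQ as secondary measures. The precision statement counts every participant: "A sample size of 30 will provide 80% power to detect an average standardized response mean (effect size for change) of 0.38".

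The same section evaluates feasibility in the whole group of 30, by the proportions of sessions attended and homework completed. The opening of STUDY DESIGN says that B-CAM is also the parent cohort's primary outcome and that the cohort is followed every 9 months for 27 months. The plan does not define completion of GMT, an analysis set, a method for missing scores or an allowance for dropout.

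**The concern.** The visit trigger is an event after baseline that the training itself can influence. A person who leaves partway never reaches it, so the scores specific to the sub-study are never scheduled. This goes further than an unwritten missing-data policy: no method chosen at the analysis stage can recover measurements that nobody planned to take.

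The plan expects attendance to vary, since it makes attendance a feasibility outcome. Feasibility would then describe all 30 people, while the effect estimate describes those who finish. People who leave a programme of weekly two-hour sessions with homework may well differ in how much they gain. Clinical Significance says that the pilot will inform a full randomized trial. If completers gained more than stoppers, a trial sized on their change would be too small for everyone who starts.

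**Working it through.** **1. The plan's own figure.** Inputs from Analysis and Sample Size: n = 30, SRM (standardized response mean) = 0.38, and two-sided 5%, because "A 95% CI that excludes 0 indicates statistically significant change".

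Power ≈ Φ(SRM × √n − 1.96)

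- n = 30: Φ(0.38 × 5.477 − 1.960) = Φ(0.121) = 54.8%; noncentral t, 52.1%.
- n = 54: Φ(0.38 × 7.348 − 1.960) = Φ(0.832) = 79.7%; noncentral t, 78.3%.

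The stated 80% does not reproduce with 30 people. It reproduces with the 54 effective observations that the plan derives for its five-measure responder analysis ("Hence the number of observations effectively available for analysis is 30 x 1.8 or 54"). That is a separate matter. Here it means only that the mean-change analysis has no spare power to absorb losses.

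**2. Which scores an early stopper would have.**

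| Measure | Planned post score after early stopping |
|---|---|
| SART, Tower of London, DEX | None; the only repeat is tied to completing GMT |
| B-CAM | No sub-study visit; possibly a 9-monthly cohort value, with no stated use |
| PDQ | Not stated |

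**3. Size of a possible bias.** Let d be the proportion who stop and r the stoppers' mean change divided by the completers' mean change. Neither is in the documents; both are assumed. The all-starter mean is (1 − d) + d × r times the completer mean, so

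completer mean ÷ all-starter mean = 1 / [(1 − d) + d × r]

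| Stoppers' change | d = 10% | d = 20% | d = 30% |
|---|---|---|---|
| None (r = 0) | 1/0.90 = 1.11 | 1/0.80 = 1.25 | 1/0.70 = 1.43 |
| Half (r = 0.5) | 1/0.95 = 1.05 | 1/0.90 = 1.11 | 1/0.85 = 1.18 |
| Equal (r = 1) | 1.00 | 1.00 | 1.00 |
| More (0.50 against 0.38) | 0.97 | 0.94 | 0.91 |

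Reading these as SRMs needs a common SD of change. On that assumption, a completer SRM of 0.38 with non-changing stoppers corresponds to 0.342, 0.304 and 0.266 in all starters (0.38 × 0.9, 0.8 and 0.7).

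**4. Precision after losses** (one-sample noncentral t, two-sided 5%).

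| People with a change score | Power at SRM 0.38 | Detectable SRM at 80% power |
|---|---|---|
| 30 | 52% | 0.53 |
| 27 (10% lost) | 48% | 0.56 |
| 24 (20% lost) | 43% | 0.60 |
| 21 (30% lost) | 38% | 0.64 |

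Keeping 30 people with change scores under the same losses would take 30/(1 − d) starters: 34, 38 or 43.

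**The case against.** Three stronger readings are tempting, and the documents do not support them.

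- **That the analysis is defined on completers.** The text says that the analysis follows completion by all persons and that change is calculated for each person. This presumes full completion and excludes nobody. Completion is also undefined, so a person who misses sessions but reaches the end of the programme may well be tested. The restriction arises by default, once someone stops.
- **That stoppers have no post score at all.** This is too broad for the primary cognitive outcome. Cohort follow-up has no stated link to GMT, so a person who leaves GMT but stays in +BHN could have a later B-CAM. What remains is that its timing would differ and that the plan does not say it would be used.
- **That the effect is overestimated.** Direction and size depend on figures the plan does not give. Zero change in stoppers is a pessimistic assumption: participants are selected partly for low B-CAM scores and then retested, so regression to the mean and practice could raise stoppers' scores too. With equal change there is no bias, and with greater change in stoppers the bias reverses.

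It can also be said that this is a pilot seeking preliminary evidence and that attendance is reported for all 30, so poor adherence would be visible. That limits the seriousness. It does not supply an assessment or an analysis rule for people who stop.

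**Conclusion.** The point holds in this form: the plan ties its only post-test to completing GMT and has no assessment or analysis rule for early stoppers. If all 30 finish, nothing is lost. Otherwise, followed as written, the within-person estimate rests on completers for SART, Tower of London and DEX, and for B-CAM too unless cohort values are brought in by a rule that the plan lacks.

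Upward bias is likely but not shown. Under an assumed 10–30% non-completion, the overstatement of the mean is 11–43% if stoppers do not change, 5–18% if they change half as much, and nil if they change equally. The detectable SRM rises from about 0.53 to as much as 0.64. The change should be made before follow-up begins, because it cannot be made afterwards.

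**What to change.** Time the post-test from the scheduled end of the person's training group, counted in calendar time from that group's first session. Apply it to everyone with a baseline test, whatever number of sessions they attended. The background section and the Intervention section give different programme lengths (seven weeks and nine weeks); these must be reconciled before the window can be written.

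In the analysis section:

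- Make everyone with a baseline test the main set for the within-person analysis, and state how missing scores are handled.
- Say whether the B-CAM from the next +BHN visit is a fallback when the extra visit is refused or only a sensitivity analysis, and acknowledge its different timing.
- Define completion, and report completers as a sensitivity analysis.
- State a dropout allowance and restate the precision for the number expected to have change scores.

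The cost is protocol wording and some effort to retest people who have stopped. A second visit is already foreseen for each participant; the documents contain no budget, so no monetary figure can be given. The downside is a probably smaller estimate, but one that describes everyone who starts the training.

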program targets executive dysfunction, which is a central problem in HIV-associated neurocognitive disorder (8, 9). GMT is grounded in a neurobiological framework and was developed based on nearly two decades of research on practical approaches to minimizing the impact of executive dysfunction, aiming to help people with brain injury manage real life tasks. The program teaches self-management principles, stress management and mindfulness, and trains participants in the use of several explicit strategies to reduce cognitive load in everyday tasks, and methods to cue attention to maintain focus on specific tasks. GMT is now a manualized protocol with set content conveyed through a combination of slides and a workbook. Two-hour small group sessions are led, in person, by a trained therapist either once twice a week, for seven weeks. The small group sessions allow participants to learn from each other, enhancing engagement. GMT has been shown to improve cognitive function in a variety of neurological conditions, as well as in healthy older people with cognitive concerns (10-13). Evidence from randomized trials shows that this intervention leads to (i) significant improvements in performance on cognitive tests, including naturalistic tests of real life tasks, (ii) reduced self-reported cognitive concerns (10, 11, 14), and (iii) significant improvements in everyday function (11-13, 15) compared to either a wait-list condition or a general brain health education control. Positive effects have been found in older people with cognitive concerns, and neurological populations with mild cognitive impairment including mild traumatic brain injury (10), stroke (11) and spina bifida (14, 15). These improvements have been shown to last at least 6 months in some studies (13-15) and are accompanied by changes in the brain networks underlying executive function (16). GMT is thus a well-validated, high yield intervention with which to test the potential of cognitive rehabilitation in older HIV+ people with cognitive concerns.

Clinical Significance

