This is a concurrently controlled trial. Study participants will be randomly selected from those participating in the ongoing, longitudinal +BHN study at 2 sites in Montreal (The Montreal Chest Institute and L'Actuel Medical Clinic). This CIHR Team Grant-supported observational, prospective cohort study is enrolling consecutive patients attending 5 HIV clinics across Canada for a total sample of 900, followed every 9 months for 27 months. Inclusion criteria are: age 35 y or older, HIV infection for at least 1 year, able to communicate in English or French and capable of providing informed consent. Exclusions are presence of dementia, life expectancy < 3 y, other neurological disorder including active opportunistic CNS infection, psychotic disorder, current substance dependence or abuse, and Hepatitis C requiring interferon therapy during the study period. Montreal sites will enroll 350 participants, which should provide an adequate pool for recruitment to this sub-study.

The GMT intervention will be tested in a randomly selected sub-group (N=30) of this cohort who meet the following additional criteria: over age 45, subjective complaints of cognitive difficulties, and performance on objective computerized cognitive tests that falls at or below the 50th percentile of performance in the cohort as a whole (as measured by the cohort study's primary outcome, a combination of self-report and performance items called the Brief Cognitive Ability Measure [B-CAM] (17)). The concurrent control group will be comprised of those eligible for GMT but not randomly selected.

Procedure

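### GMT is delivered in small groups, but no analysis allows for correlation between members of the same group, so the intervals for the GMT effect are too narrow if that correlation is positive

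*Combined protocol and SAP*

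**What the plan says.** **Delivery.** The Intervention section states that the programme "involves 9 weekly 2-hour small group sessions led by a trained therapist". Interaction between members is part of the design: the sessions "explicitly encourage participants to share their challenges and successes with others in the group to promote learning and engagement". The Background makes the same point: "The small group sessions allow participants to learn from each other, enhancing engagement".

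**Within-person analysis.** Under Analysis and Sample Size, "change from pre-to post will be calculated for each person and a 95% confidence interval (CI) around the mean change will be calculated", followed by the decision rule "A 95% CI that excludes 0 indicates statistically significant change". There is one change score per person and no term for training group.

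**GEE analyses.** For the responder analysis, "generalized estimating equations (GEE) will be utilized to adjust for a possible correlation between the different measures". The between-group analysis uses GEE for a continuous outcome with the same stated purpose.

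**Design effect.** The only one in the plan, 1.8, concerns five measures within a person with an assumed correlation of 0.2.

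**Not stated.** The documents do not give the size or number of training groups, the number of therapists, an ICC for change within groups, or a group identifier. Subject IDs are carried over from the parent cohort.

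**The concern.** People trained together share sessions, a therapist and group discussion. If some groups do better than others, members' changes are correlated, and 30 people carry less information about the mean change than 30 independent people would. The standard error of a simple mean of change scores does not reflect this.

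The GEE does not fill the gap. Its stated purpose is correlation between measures, so its cluster is the person. Two people from the same training group are still treated as independent.

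What is mainly at stake is the within-person result. The plan labels the between-group comparison exploratory, but it reads statistical significance directly from the within-person CI, and the pilot is meant to inform a full trial. A CI that narrowly excludes 0 could be reported as significant change when an interval allowing for groups would include 0.

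**Working it through.** **Inputs from the documents.** n = 30 receive GMT. The interval is two-sided 95%. The analysis is the mean of individual changes.

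**Inputs assumed.** Group size m of 5, 6 or 10 (6, 5 or 3 groups) and ICC of 0, 0.02, 0.05 or 0.10.

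**Step 1: the plan's own figures.**
- Design effect for measures: 1 + (5 − 1) × 0.2 = 1.8, and 30 × 1.8 = 54. Both match the plan. Neither concerns training groups.
- Power at a standardized response mean (SRM) of 0.38 with n = 30: Φ(0.38 × √30 − 1.96) = Φ(0.12) = 54.8%, against the stated 80%. With n = 54 it is Φ(0.38 × √54 − 1.96) = Φ(0.83) = 79.7%. The stated figure therefore fits 54 rather than 30. This discrepancy exists with no group clustering at all and is a separate problem.

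**Step 2: effect of training groups.**
- Design effect: DE = 1 + (m − 1) × ICC
- Correct SE ÷ planned SE = √DE
- Effective n = 30 ÷ DE
- Actual error of a nominal 5% test = 2 × [1 − Φ(1.96 ÷ √DE)]

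| m | ICC | DE | Correct SE larger by | Effective n | Actual error |
|---|---|---|---|---|---|
| any | 0 | 1.00 | 0% | 30.0 | 5.0% |
| 5 | 0.02 | 1.08 | 4% | 27.8 | 5.9% |
| 5 | 0.05 | 1.20 | 10% | 25.0 | 7.4% |
| 5 | 0.10 | 1.40 | 18% | 21.4 | 9.8% |
| 6 | 0.02 | 1.10 | 5% | 27.3 | 6.2% |
| 6 | 0.05 | 1.25 | 12% | 24.0 | 8.0% |
| 6 | 0.10 | 1.50 | 22% | 20.0 | 11.0% |
| 10 | 0.02 | 1.18 | 9% | 25.4 | 7.1% |
| 10 | 0.05 | 1.45 | 20% | 20.7 | 10.4% |
| 10 | 0.10 | 1.90 | 38% | 15.8 | 15.5% |

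Example for m = 6, ICC = 0.05: DE = 1 + 5 × 0.05 = 1.25; √1.25 = 1.118; 1.96 ÷ 1.118 = 1.753; two-sided error 8.0%.

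Relative to the correct SE, the planned SE is short by 1 − 1/√1.08 = 4% to 1 − 1/√1.90 = 27%.

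A simulation of the planned analysis (30 people, ordinary one-sample t interval, no true effect) agrees: 5.9% error at m = 5, ICC 0.02; 8.0% at m = 6, ICC 0.05; 10.3% at m = 10, ICC 0.05; 15.6% at m = 10, ICC 0.10.

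**Step 3: what a group-level model would cost.** With k groups there are about k − 1 degrees of freedom. The 97.5% t quantile is 2.05 with 29 df, 2.57 with 5 df (6 groups) and 4.30 with 2 df (3 groups). The multiplier alone therefore grows by a factor of 1.26 to 2.10. In simulation with a true ICC of 0.05 and 3 to 6 groups, the ANOVA estimate of the ICC was zero or negative in 43% to 47% of runs, with a 95% range of about −0.19 to 0.37.

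**The case against.** **No ICC is documented.** A reader might infer that the intervals are certainly too narrow. The documents do not support that. The conclusion needs a positive within-group ICC, and several features work against large differences between groups: a manualized programme, a standard workbook, tailoring to individual challenges, and audiotape review for adherence. A shared therapist separates groups only if there is more than one therapist, and the number is not stated. If inference is confined to the groups actually run, the person-level CI is not too short. All of this stands, so the point is conditional. It does not remove the concern, because learning within the group is an intended mechanism and the plan gives no reason to assume that the ICC is zero.

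**The upper end is extreme.** The 38% figure needs groups of 10, which stretches the word small, together with an ICC of 0.10. With groups of 5 or 6 and an ICC of 0.02 to 0.05, the correct SE is 4% to 12% larger. This also stands.

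**It is a pilot.** The first objective is feasibility and acceptability, and the between-group comparison is exploratory. That limits the consequence, but the within-person CI still carries an explicit significance rule.

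**The remedy may cost more than the problem.** With 3 to 6 groups, a random-intercept model as the main analysis would have 2 to 5 degrees of freedom, and over most of the assumed range the wider t multiplier would outweigh the variance inflation being corrected. Nor could this pilot give the full trial a usable ICC. Both objections stand and decide the form of the fix.

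**Conclusion.** The plan allows for no correlation between people in the same training group in any analysis. If the within-group ICC of change is positive, the intervals for the GMT effect are too narrow and the significance rule is anti-conservative. Under the assumed range (groups of 5 to 10, ICC 0.02 to 0.10), the correct SE is 4% to 38% larger than the planned one, and a nominal 5% test runs at about 6% to 15%. Group size and ICC are assumptions, not figures from the documents.

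In the between-group comparison the inflation applies to the GMT arm only, since controls are not trained in groups.

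A reader who sets the stated SRM of 0.38 beside a detectable value adjusted for groups might put the whole gap down to clustering. That would be wrong: by the normal approximation, n = 30 gives a detectable SRM of about 0.51 (2.80 ÷ √30) before any clustering enters.

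The point is a cheap improvement worth making. Its weight comes from the fact that the stated rule, followed as written, can declare significance too readily.

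**What to change.** 1. Record training group and therapist for every GMT participant, and report the number and size of groups.
2. Keep the person-level CI. Beside it, report the CI for mean change widened by √(1 + (m − 1) × ICC) over a prespecified ICC range, for example 0 to 0.10. Call the change statistically significant only with a statement of whether it survives that range.
3. In the exploratory between-group analysis, add a partially nested sensitivity model, with a group effect in the GMT arm only and controls as singletons, using small-sample degrees of freedom.
4. Report any ICC estimate with its CI, and describe it as imprecise.

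**Cost.** One or two data fields, a short addition to the analysis and somewhat wider intervals. Recording must be prospective, because nothing in the plan ensures that group membership can be recovered later. With about 3 to 6 groups the group-level model has few degrees of freedom, so it should supplement the main analysis and not replace it.
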